1.1 Background

Hepatitis D is caused by a defective RNA-virus, that is known to be among the smallest human pathogenic viruses. As it partly shares the viral entry into hepatocytes with HBV, a coinfection is mandatory (1). Besides a simultaneous infection with HBV and HDV, it might also occur in the sense of a superinfection to a preexisting HBV-infection (2). Though most of the acute infections recover spontaneously, a progression to chronic disease is well described (3). The persistence of HDV leads to an accelerated fibrosis progression and eventually to cirrhosis and an increased risk of developing hepatocellular carcinoma (HCC) as well (4, 5). With the widely established feasibility of immunization against viral Hepatitis B, numbers of HDV-infection in high-income countries are quite low. Nevertheless, the burden of chronic HDV-infection worldwide is high, as different studies estimate the number of patients from 12 million to up to 72 million (6-8).

In the subgroup of people living with HIV (PLWH), who are at increased risk for acquiring viral hepatitis in general, rates of HDV infection have been reported between 10%-20% of HIV/HBV-coinfected people, with variations according to region as well as transmission group. Particularly, early in the HV epidemic higher rates of HDV have been reported for HIV/HBV coinfected drug users. More recently, a shift from people who acquired HIV through drug injection (PWID) to men who have sex with men (MSM) has been reported with HDV coinfection rates of around 8% (9). Common for all PLWH with HBV/HDV-coinfection is a more rapid progression in liver disease (10), resulting in increased rates of decompensated cirrhosis and higher mortality (11, 12). Therefore, mandatory screening for HDV was implemented into current EACS guideline recommendations. However, there is still a lack of testing in daily routine, even at sites where testing is easily accessible and reimbursed. Moreover, most PLWH

who are coinfecte with HBV are tested at initial HBV diagnosis, but after being put on antiretroviral treatment, which usually includes a tenofovir-based therapy a follow-up testing of HDV does not take place routinely.

1.2 Objective

The aim of this project is to set up a cross-sectional cohort study (France, Germany, The Netherlands, Poland, Spain, Switzerland, Italy, United Kingdom and Portugal) to assess the implementation of EACS guidelines for HDV-testing among PLWH with positive HbsAg and thereby evaluate the prevalence of HDV infection among HIV/HBV-coinfected in 2023, as well as corresponding risk factors. In addition to the testing itself, this study will also set up a cohort and database for future HDV studies among PLWH, including clinical, virological und laboratory parameters.

1. Analyze the rate of HDV-testing and evaluate the prevalence of HDV-infection by testing.
 - a. Evaluation of former screening of HDV by assessing existing data at study sites.
 - b. Determination of the HDV prevalence in European PLWH and HBV coinfection.
2. Setting up a database of all PLWH with HBV/HDV coinfection
 - a. Analysis of transmission risk factors for HDV coinfection
 - b. Asses the rate of HDV positive patients with ongoing HDV replication.
 - c. Define the liver disease state by APRI score, fibroscan, ultrasound and routine laboratory test results.

2.Cohort Design and Methods

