2.1 General

In this multi-center cohort study patients with documented HIV/HBV-coinfection (2 measurements of positive HBsAg > 6month interval and Anti-HBc-positive) will be evaluated for past HDV screening (last 24 months).

Eligible participants must be 18 years of age or older.

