2.3 Accrual goal

A cohort of 8000 HIV/HBV-coinfected individuals with serological HDV-screening evidence.

3. Patient Inclusion and Exclusion Criteria

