7.4. Data Management

Data security will be assured for all patients participating in the study. All data management will be performed according to GCP. Data analysis will be performed by [name] (cooperating scientist; Amsterdam University Medical Centers) conducting to GCP.

8. Milestones

The patients being recruited are already tied to the different center sites and preexisting data are available. After writing consent, a retrospective analysis of these data can take place. Recruitment of patients is planned to run from November 2023 until April 2024.

MS	Title	Work pkg. (nr.)	Institution	Date (dd.mm.yyyy)	Proof of achievement/fulfillment
1	Study protocol for multicentric approach	1	University Hospital Bonn	15.11.2023	Study protocol
2	Ethics approval	1	University Hospital Bonn	30.11.2023	Ethics approval achieved
3	Agreement with cooperating centers	1	University Hospital Bonn	XX.XX.2023	Signed agreement
4	Start of patient enrolment	2 and 3	University hospital Bonn cooperating centers	XX.XX.2023	Electronic database established
5	Reaching 50% of respective HBs-Ag positive patients	2 and 3	University Hospital Bonn and cooperating centers	XX.XX.2024	50% of eligible/reachable patient population enrolled
6	Finishing patient acquisition	2 and 3	University Hospital Bonn and cooperating centers	XX.XX.2024	100% of patient population enrolled
9	Data Analysis	4	University Hospital Bonn and cooperating centers. Final data analyses by University Medical Centers Amsterdam	XX.XX.2024	Data analyses completed, and preparation of manuscript

9. Data Protection

All patient data that are used, have already been collected and country related databases have been set up. The included data are to be within the treating physicians keeping. The values that are evaluated in this study are shared with the other participating physicians, though data containing personal information are excluded from this. Collected data will be analyzed, evaluated and presented in an anonymous form, ensuring confidentiality of patient data towards third parties.

10. Literature:

2. Rizzetto M. Hepatitis D: thirty years after. *J Hepatol.* 2009;50(5):1043-50.

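### HDV status comes from incomplete routine-care testing, so the crude ratio in 5.1 does not estimate prevalence in all HIV/HBV-coinfected persons if testing differs across groups

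*Protocol*

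**What the plan says.** **Target.** Protocol section 1.2 sets out to assess implementation of the testing guideline "and thereby evaluate the prevalence of HDV infection among HIV/HBV-coinfected in 2023". Objective 1b is "Determination of the HDV prevalence in European PLWH and HBV coinfection". Both name all coinfected persons, not those whom a clinician chose to test.

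**Source of HDV status.** Objective 1a is "Evaluation of former screening of HDV by assessing existing data at study sites". Under section 2.1, patients "will be evaluated for past HDV screening (last 24 months" (the parenthesis closes there). Section 4 uses one database both to see whether screening was done and to determine prevalence. Section 9 (Data Protection) states: "All patient data that are used, have already been collected and country related databases have been set up".

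**Testing and HDV rates.** Section 1.1 says that HDV testing is lacking in daily routine, that most coinfected persons are tested when HBV is first diagnosed, and that repeat testing is not routine. It gives HDV rates of 10% to 20% "with variations according to region as well as transmission group", and around 8% for men who have sex with men.

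**Cohort and estimator.** Section 2.3 sets the goal as "A cohort of 8000 HIV/HBV-coinfected individuals with serological HDV-screening evidence". Section 5.1 defines prevalence as HDV-positive persons over all HBV/HIV individuals in the database. Section 5 provides for descriptive statistics only.

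**The concern.** A prevalence built on tests ordered in routine care describes the target population only if testing is complete or is unrelated to HDV. The protocol says it is not complete, and it gives no reason to treat those tested as a random sample. It also says that HDV differs by region and transmission group. If testing differs along the same lines, the mix of tested persons is not the mix of all coinfected persons.

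Section 5.1 has no step for this, and the protocol leaves the denominator open. Objective 1 and section 4 need untested persons in the database. Section 2.3 describes a cohort of screened persons, in which the testing rate would be 100% by construction. Settling the denominator alone does not settle the matter: moving from all persons to tested persons replaces one bias with another.

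At stake are the headline prevalence and any comparison of countries, which could partly reflect testing habits. A sample of 8000 does not help, because size narrows the interval without removing selection.

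**Working it through.** **The plan's own figure.** Section 2.2: 800,000 × 0.05 = 40,000 coinfected persons, and 40,000 × 0.20 = 8000. This reproduces; the country figures sum to 800,000 if Spain is read as 150,000. The protocol gives neither the fraction tested nor the testing pattern, so no corrected prevalence can be computed. Everything below uses assumed inputs.

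**Formulas.** For stratum k let w be its share of all eligible persons, p its HDV prevalence and c its testing coverage, with testing unrelated to HDV within the stratum.
- True prevalence: Σwp
- Section 5.1 with untested persons in the denominator: Σwpc
- Restricted to persons with a result: Σwpc / Σwc
- Standardised: Σw × (proportion positive among tested in the stratum), which equals Σwp under the stated condition

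**Assumed example.** Group A: w = 0.3, p = 0.20. Group B: w = 0.7, p = 0.05. True prevalence = 0.3×0.20 + 0.7×0.05 = 9.5%.

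At coverage 80% (A) and 40% (B), positives found are 0.3×0.8×0.20 + 0.7×0.4×0.05 = 0.062 and persons tested are 0.3×0.8 + 0.7×0.4 = 0.52. The all-database ratio is 6.2%; the tested-only ratio is 0.062/0.52 = 11.9%. Other patterns, computed the same way:

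| Coverage A / B | Overall coverage | All-database | Tested-only |
|---|---|---|---|
| 80% / 40% | 52% | 6.2% | 0.062/0.52 = 11.9% |
| 80% / 20% | 38% | 5.5% | 0.055/0.38 = 14.5% |
| 60% / 50% | 53% | 5.35% | 0.0535/0.53 = 10.1% |
| 40% / 20% | 26% | 3.1% | 0.031/0.26 = 11.9% |
| 20% / 20% | 20% | 1.9% | 0.019/0.20 = 9.5% |
| 40% / 80% | 68% | 5.2% | 0.052/0.68 = 7.6% |

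The standardised figure is 9.5% in every row, because the example lets testing depend only on the strata. Three things follow:
- The all-database ratio is too low in every row, even where testing is equal across groups.
- The tested-only ratio can be too high, correct or too low.
- Its bias depends on the ratio of the coverages, not on their level: 80/40 and 40/20 both give 11.9%, and 20/20 gives none.

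**At the protocol's expected 20%.** Let r be the testing probability of HDV-positive persons relative to HDV-negative persons. The prevalence among tested is then 0.2r / (0.2r + 0.8): 11.1% at r = 0.5, 20.0% at r = 1, 27.3% at r = 1.5 and 33.3% at r = 2. With 8000 tested, the 95% half-width is 1.96 × √(0.2×0.8/8000) = 0.88 points. An r of about 1.06 already produces a bias of that size.

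**Limit of standardising.** Assume strata with w = 0.2, p = 0.50 and w = 0.8, p = 0.125 (true 20%), with coverage 80% and 40%. The tested-only figure is 0.12/0.48 = 25.0%, and standardising returns 20.0%. If HDV-positive persons are also tested 1.5 times as often within each stratum, the stratum figures become 0.75/1.25 = 60.0% and 0.1875/1.0625 = 17.6%. The standardised figure is then 0.2×0.600 + 0.8×0.1765 = 26.1%.

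**The case against.** **Selective testing is assumed, not documented.** This stands. No section says that tests are ordered for raised transaminases or known risk. The one pattern described is timing: testing at initial HBV diagnosis. Variation of HDV between groups does not show that testing varies between them. A reader might infer that the tested-only figure must be too high; the protocol does not support that, and only the condition (if testing differs across groups) can be asserted.

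**Low coverage is not the driver of the tested-only bias.** A reader might also infer that this bias is largest in countries with low coverage. The arithmetic contradicts that, since only the coverage ratio matters, and the protocol says nothing about how that ratio differs between countries.

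**Section 5.1 literally divides by all persons.** On that reading the error is downward, not upward. This is correct, and it is why both readings have to be shown and section 2.3 reconciled with objective 1.

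**The study may do its own testing.** Objective 1 speaks of prevalence by testing, and section 5.2 says replication will be measured by PCR. But the PCR covers only seropositive persons, no section provides antibody testing for the untested, and section 9 says the data are already collected. The wording is loose, but it does not supply the missing results.

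**Weighting belongs in a SAP.** In part. Detail could be left there, but the protocol itself names a crude estimator and a screened cohort, and those determine what is estimated.

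**The example is artificial.** Its inputs are assumed, and the 5% in group B lies below the rates in sections 1.1 and 2.2. The second example, built on the expected 20%, shows the same mechanism.

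**Conclusion.** The concern holds in conditional form. The crude ratio in section 5.1 estimates prevalence in all HIV/HBV-coinfected persons only if everyone has a result or, once restricted to tested persons, if testing is unrelated to HDV. The protocol rules out the first and offers nothing for the second. With untested persons in the denominator the figure is biased downward. Restricted to persons with a result, its bias is unknown in size and direction. The 6.2% and 11.9% against a true 9.5% illustrate the mechanism under assumed inputs; they do not predict the study's result. The protocol does not support saying that a tested-only figure will be inflated, or that it will be worst where coverage is low.

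**What to change.** 1. In sections 2.3 and 5.1, state that the database holds all eligible HBsAg-positive persons, tested or not, so that section 2.3 agrees with objective 1.
2. In section 5.1, report the crude proportion positive among tested persons together with testing coverage, overall and by stratum.
3. Next to it, report a prevalence standardised to all eligible persons: the proportion positive among tested within strata of country and transmission group, weighted by each stratum's share of all eligible persons.
4. Where available, add time since HBV diagnosis and transaminases, with a missing category, since section 3.1 makes liver enzymes non-compulsory. Take both at a common index date defined in the same way for tested and untested persons. A date tied to the HDV test does not exist for the untested.
5. State that standardising removes only the bias explained by the strata.

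The cost is analysis work and a somewhat wider interval. Country is known and transmission risk is already needed for objective 2a. If sites had planned to enter screened persons only, entering the untested adds data work, but objective 1 requires those persons in any case.

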2.1 General

In this multi-center cohort study patients with documented HIV/HBV-coinfection (2 measurements of positive HBsAg > 6month interval and Anti-HBc-positive) will be evaluated for past HDV screening (last 24 months).

Eligible participants must be 18 years of age or older.

2.2 Study Centers and Accrual of Patients

To secure representative data, each cohort or clinic network will aim to enroll a sample size of at least 20% of all HIV/HBV-coinfected individuals in each country. France, Switzerland, Italy, and The Netherlands already have well established national cohorts which are representing more than 50% of all PLWH in their respective countries. In the remaining countries (Germany, Spain, Poland, Portugal, UK) well-defined cohorts in specialized HIV-clinics or networks of HIV-centers are existing, which allow for a sufficient recruitment. The overall number of participants is planned to reach at least 8000 HIV/HBV-coinfected persons. With an estimated 800.000 PLWH in the following 9 countries: Spain 150.00, France 190.000, Germany 93.000, England 106.000, Portugal 61.000, Italy 140.000, Poland 20.000, Switzerland 16.000, Netherlands 24.000, and an estimated HBV-Prevalence of 5%, this would lead to a cohort of around 40.000 HIV/HBV coinfecte individuals. According to current data, 20% of HIV/HBV-coinfected PLWH are expected to have an HDV-infection, which should add up to 8000 individuals that would be needed to be studied. This should guarantee a representative sample size and would represent a highly meaningful European cohort for future HDV studies.

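### A 20% enrolment fraction does not by itself make the cohort representative: Section 2.2 needs a rule for choosing patients, and Section 2.3 tilts accrual towards the HDV-tested

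*Protocol*

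**What the plan says.** Section 2.2 states the purpose and the means in one sentence: "To secure representative data, each cohort or clinic network will aim to enroll a sample size of at least 20% of all HIV/HBV-coinfected individuals", counted within each country. It then fixes the total: "The overall number of participants is planned to reach at least 8000 HIV/HBV-coinfected persons". The paragraph closes on the same idea: "This should guarantee a representative sample size".

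The other places that bear on who gets enrolled are these:

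- Section 2.3 (accrual goal) repeats the 8000 but describes them as people for whom there is serological evidence of HDV screening.
- Sections 2.1, 3.1 and 3.2 define eligibility by HIV infection, persistent HBsAg and age. HDV status and HDV testing are not criteria.
- Section 4 names the source (national cohorts and networks of HIV clinics) but gives no rule for picking patients within it.
- Section 8, milestone 5, is proved by "50% of eligible/reachable patient population enrolled". Milestone 6, the end of patient acquisition, is proved by "100% of patient population enrolled".
- Section 5.1 computes prevalence with everyone in the database as the denominator.

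**The concern.** Whether one fifth of a population speaks for the other four fifths depends on how that fifth was picked, not on its being a fifth. The protocol requires neither complete, random nor consecutive enrolment. A convenience sample, or one made up of patients who already have an HDV result, would satisfy Section 2.2 if it were large enough. The wording of Section 2.3 makes the second case more likely, because an untested patient does not obviously count towards the goal.

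The HDV-testing rate and the HDV prevalence are both under objective 1 in Section 1.2, and both are proportions of whoever is enrolled. If enrolment depends on HDV testing, these results describe the selection as much as the population. Countries that enrol everyone could not be compared with countries that enrol a chosen part.

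**Working it through.** **1. The plan's own figure.** Section 2.2 gives "With an estimated 800.000 PLWH in the following 9 countries". Reading the Spanish entry, which lacks a digit, as 150,000, the counts in thousands sum as 150 + 190 + 93 + 106 + 61 + 140 + 20 + 16 + 24 = 800. The section adds "an estimated HBV-Prevalence of 5%, this would lead to a cohort of around 40.000 HIV/HBV coinfecte individuals": 800,000 × 0.05 = 40,000. Then 40,000 × 0.20 = 8000, so the figure reproduces. (The section also reaches 8000 through an expected HDV prevalence of 20%. Nothing below relies on that route.)

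**2. What size buys.** The 95% half-width is 1.96 × √(p(1 − p)/8000).

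- p = 0.08: 0.6 percentage points
- p = 0.10: 0.7 points
- p = 0.20: 0.9 points

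Sampling error is therefore small, and an error from selection would not shrink as the sample grew.

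**3. Room to choose.** Section 2.2 says four national cohorts hold more than 50% of people living with HIV in their countries. If the HBV share inside the cohort equals the national share (assumption), the 20% target is less than 0.20/0.50 = 40% of the coinfected patients the cohort holds. More than 60% could be left out with the target met, and no text says which. For the other five countries the protocol does not give the share held by the sites, so the room to choose there is unknown.

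**4. Effect on the testing rate.** Let T be the true testing rate and k the relative chance that a tested patient is enrolled. Neither is in the protocol; both are assumed. Reported rate = kT/(kT + 1 − T). With T = 0.40:

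| k | Reported testing rate |
|---|---|
| 1 | 40.0% |
| 1.5 | 0.60/1.20 = 50.0% |
| 2 | 0.80/1.40 = 57.1% |
| 3 | 1.20/1.80 = 66.7% |

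If only tested patients are enrolled, the reported rate is 100% whatever T is.

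**5. Effect on prevalence.** Assume a true prevalence of 10%, T = 0.40, k = 2, and HDV twice as common in tested as in untested patients. Prevalence in the untested is 0.10/(0.40 × 2 + 0.60) = 7.1%, and in the tested 14.3%. Tested patients make up 57.1% of those enrolled.

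- Untested participants are later tested: 0.571 × 14.3% + 0.429 × 7.1% = 11.2%, above the truth.
- They stay untested and count as non-cases in the Section 5.1 denominator: 0.571 × 14.3% = 8.2%, below the truth.

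If only tested patients are enrolled, with 20% to 50% of patients tested and HDV 1.5 to 3 times as common in the tested, a true 10% is reported as 12.0% (0.10/1.25 × 1.5) to 21.4% (0.10/1.40 × 3). If HDV is equally common in both groups, tested-only enrolment gives 10% and no bias.

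**The case against.** The strongest defence is that the milestones already give the rule: sites enrol all their eligible patients, and 20% is merely the national coverage this should achieve. That reading is possible, and under it selection within sites would largely disappear. But Section 2.2 does not say it, milestone 5 uses an undefined *reachable* population, and milestone 6 could equally mean progress to the planned total. The defence shows what the protocol may intend, not what it fixes.

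Three stronger readings are tempting, and the protocol does not support them.

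- *The milestones contradict the 20%.* They do not. The 20% is a minimum on a national denominator, and it is compatible with enrolling every eligible patient at the participating sites. The word *reachable* stands in milestone 5 only.
- *Sites are led to pick HDV-positive patients because the cohort is to serve future HDV studies.* The protocol gives no such instruction. Eligibility ignores HDV, and Sections 2.1 and 4 have patients assessed for whether screening took place, which implies that untested patients belong in the study. The only text found to favour tested patients is Section 2.3.
- *Prevalence must be biased upward.* A reader might double the chance of enrolment for HDV-positives and turn 10% into 0.20/1.10 = 18.2%. That assumes selection on HDV status and a known status for everyone enrolled. The protocol states neither, and step 5 of the working shows that the reported figure can also fall below the truth.

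It is also fair to say that complete enrolment cannot be promised: Section 7.3 requires written consent, and Section 3.1 accepts existing cohort consent only where adequate. This shapes the remedy but does not remove the gap. Who is enrolled is a matter for the protocol, and an analysis plan cannot reliably repair it without a record of the eligible patients.

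**Conclusion.** The point holds as a design weakness that should be corrected. The arithmetic behind 8000 is right on its inputs, but the protocol credits that number with a representativeness that only a selection rule can give, and it contains no clear rule. Section 2.3 adds a pull towards tested patients that conflicts with measuring the testing rate.

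Sampling error is about 0.6 to 0.9 points. Under the assumed preferences of 1.5 to 3, the testing rate would be overstated by 10 to 27 points from a true 40%. The distortion of prevalence depends on how HDV relates to testing and on whether untested participants are later tested, so no single size or direction can be given. The preference ratios, the 40% and the 10% are illustrations; the protocol permits such selection but does not prescribe it. If every site includes all its eligible patients, the problem within sites largely goes away.

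**What to change.** - **Section 2.2:** state that each site lists all patients meeting Section 3 at an index date, irrespective of HDV test status or result. It then includes all of them for whom consent is available, whether new or adequate existing cohort consent. Where that is not feasible, it takes a random or consecutive sample from the list. Keep 20% as a country coverage target only, and remove the statements that it secures or guarantees representativeness.
- **Section 2.3:** count accrual as HIV/HBV-coinfected individuals whether or not they have been screened for HDV.
- **Section 8:** define *reachable* in milestone 5 and use the same denominator in milestone 6.
- **Reporting:** give the numbers listed, approached and enrolled for each site, so that any loss through consent or contact is visible.

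The cost is a listing query and a log at each site, and some added consent effort. Sites lose the freedom to enrol whoever is most convenient.

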3.2. Exclusion-Criteria

PLWH with a cleared HBV-infection will be considered as HIV-monoinfected persons. Individuals younger than 18 years of age will be excluded from the analysis.

Patients with any social condition or living circumstances which may interfere with the conduct of the study, as anticipated by the investigator, such as incapacity to adequately understand the study content or not willing to cooperate will be excluded from the study.

For France, patients without adequate social security will be excluded.

4. Study Procedures

All participating PLWH will be recruited from the already existing national cohorts and defined networks of specialized HIV-clinics, respectively. This database will allow for the initial analysis of whether HDV screening was performed and allow to determine the HDV prevalence in the participating countries as well as study risk factors for HDV transmission.

Only patients who were alive in 2022 will be included into the study.

5. Plan of Analysis

Because of the observational nature of the study no predefined statistical power calculations can be made. Descriptive statistics will be used.

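### Source type is nested in country, and a 20% enrolment target does not make the data from the five clinic or network countries representative, so their testing rate and prevalence cannot be assumed to be national figures

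*Protocol*

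**What the plan says.** Section 2.2 of the protocol names two kinds of source. For four countries it states coverage: "France, Switzerland, Italy, and The Netherlands already have well established national cohorts which are representing more than 50% of all PLWH in their respective countries". For the other five it gives the type of source but no share of the country's PLWH: "In the remaining countries (Germany, Spain, Poland, Portugal, UK) well-defined cohorts in specialized HIV-clinics or networks of HIV-centers are existing". It adds only that these sources permit enough recruitment. Section 4 repeats the division between national cohorts and clinic networks. No country is given both.

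Representativeness is tied to numbers. Section 2.2 says: "To secure representative data, each cohort or clinic network will aim to enroll a sample size of at least 20" per cent of each country's HIV/HBV-coinfected individuals. Of the resulting total it says: "This should guarantee a representative sample size and would represent a highly meaningful European cohort for future HDV studies".

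The intended use goes beyond the centres. Section 4 says that the database will "allow to determine the HDV prevalence in the participating countries". Section 1.2 aims at HDV prevalence in European PLWH with HBV and at how far the testing guideline is implemented, the latter from existing data at the study sites. Section 5.1 divides HDV-positive persons by all HIV/HBV individuals in the database. No weighting or separation by source is stated.

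**The concern.** The protocol infers representativeness from the size of the sample. A larger share of a country's patients narrows the confidence interval. It does not make those patients resemble the ones outside the contributing centres. For four countries the reader at least knows that the source covers more than half of PLWH. For the other five neither coverage nor a rule for choosing centres is given.

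Both main quantities could depend on which centres contribute. Section 1.1 reports HDV rates of 10% to 20% among HIV/HBV-coinfected people, varying by region and transmission group, and around 8% in the setting of more recent transmission among men who have sex with men. A centre's patient mix can therefore move its prevalence. Testing is a practice of the centre, so the testing rate depends on which centres are included.

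Because source type is fixed by country, the database cannot separate the two. What is at stake is whether figures for Germany, Spain, Poland, Portugal and the UK, and a pooled European figure in which they carry much of the weight, may be read as describing populations or only the contributing centres.

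**Working it through.** **Inputs from Section 2.2 (thousands of PLWH).** Spain 150 (printed with a digit missing; read as 150,000, which the stated total requires), France 190, Germany 93, England 106 (used for the UK), Portugal 61, Italy 140, Poland 20, Switzerland 16, Netherlands 24. HBV prevalence 5%. Enrolment target at least 20%.

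**Reproducing the plan's figure.** 150 + 190 + 93 + 106 + 61 + 140 + 20 + 16 + 24 = 800. Then 800,000 × 0.05 = 40,000 coinfected, and 40,000 × 0.20 = 8,000. This agrees with the protocol.

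**Split by source type.**

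| Source | PLWH | Share | Coinfected (5%) | At 20% enrolment |
|---|---|---|---|---|
| National cohorts (190 + 16 + 140 + 24) | 370,000 | 46.25% | 18,500 | 3,700 |
| Clinics or networks (150 + 93 + 106 + 61 + 20) | 430,000 | 53.75% | 21,500 | 4,300 |

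The 20% is a minimum. If the national cohorts enrolled 50% and the networks 20% (assumption), the counts would be 18,500 × 0.50 = 9,250 and 4,300. The five countries would then supply 4,300 / 13,550 = 32% of the sample against 54% of the population.

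**What the 20% target controls.** The half-width is 1.96 × √(p(1 − p)/n). At a prevalence of 20%, Germany (n = 930) has ±2.6 points, Poland (n = 200) ±5.5 points, and the five countries together (n = 4,300) ±1.2 points.

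**What it does not control.** Let f be the share of a country's coinfected patients held by the source, p the prevalence among them and q the prevalence among the rest. Assume that those enrolled represent those held. The country value is fp + (1 − f)q, so the bias of reporting p is (1 − f)(p − q). For illustration, take p and q from the ends of the 10% to 20% range in Section 1.1. Which end belongs to which group is an assumption, and so is f.

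| f | p = 20%, q = 10% | p = q | p = 10%, q = 20% |
|---|---|---|---|
| 20% | +8 points | 0 | −8 points |
| 50% | +5 points | 0 | −5 points |
| 80% | +2 points | 0 | −2 points |

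Sample size does not enter this formula. Coverage does, and it is the quantity not stated for the five countries.

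**Effect on a pooled testing rate.** If the rate at the centres differs from the country rate by d points, the five countries' contribution to the pooled error is w × d, where w is their share of the sample. With d assumed to be 5 to 20 points in either direction, w = 0.5375 gives 2.7 to 10.8 points and w = 0.32 gives 1.6 to 6.3 points. The sampling half-width at N = 8,000 and a rate of 50% is 1.96 × √(0.25/8,000) = 1.1 points. This treats the national cohorts as unbiased, which the protocol does not establish.

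**The case against.** The case against has five parts.

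- **Networks may be broad.** Section 2.2 names networks of HIV centres as well as specialised clinics, and a network could carry most of a country's HIV care. A reader might infer that the figures from the five countries are not national. The documents do not show that. They show only that national validity is not established.
- **A common denominator exists.** The 20% target is set against all coinfected persons in each country. This is true, and if met it puts a floor under coverage. It does not show that the enrolled fifth resembles the rest.
- **The contrast is one of degree.** The national cohorts are described only as covering more than half of PLWH, and nothing says that they recruit outside specialised centres. This stands. By the formula above they too can be biased, though with smaller (1 − f) than a source at the 20% floor.
- **The direction is unknown.** A reader might infer that specialised centres test more or see more HDV, so that the figures are too high. The protocol does not say so. Section 1.1 observes that "there is still a lack of testing in daily routine, even at sites where testing is easily accessible and reimbursed", which gives no support for higher testing at such centres.
- **No country comparison is planned.** A reader might infer that a contrast such as Germany with France is confounded by design. It would be, but the protocol plans only descriptive results, with prevalence taken over the whole database. The Section 4 phrase about participating countries attaches to prevalence, not testing, and can be read as the nine together.

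Stratified tables could also sit in a statistical analysis plan that is not shown. But the choice of sources and the argument from size to representativeness are made in the protocol itself, and that part of the point remains.

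**Conclusion.** The point holds in a limited form. Source type is nested in country. Coverage is stated for four countries and not for the five that hold 53.75% of PLWH by the protocol's own counts (4,300 of 8,000 if every country enrols 20%). Enrolling 20% does not by itself make the data representative, so testing rate and prevalence in those five countries cannot be assumed to be national figures.

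No bias is demonstrated. Its sign and size are unknown. It is zero if patients outside the centres do not differ, and it shrinks as coverage rises. The bias figures in points are illustrations on assumed inputs, not estimates. This is a cheap improvement that limits what the study may conclude. It is not a flaw that invalidates the study.

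**What to change.** Change Sections 2.2, 4 and 5.1 as follows.

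1. In Section 2.2, drop the argument that sample size secures or guarantees representativeness, and state that the 20% target serves precision.
2. Record the source type of every contributing site and, for every country, the share of PLWH covered by the source.
3. In Section 5.1, report testing rate and HDV prevalence separately for the national-cohort countries and the clinic or network countries, beside the pooled figure.
4. In Section 4, describe results from Germany, Spain, Poland, Portugal and the UK as those of patients in care at the participating centres, unless coverage is shown.
5. Add a sensitivity analysis restricted to the national cohorts. Because this also changes which countries are included, a difference from the pooled figure should not be attributed to source type alone.

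The cost is one variable per site, one coverage figure per country, some wording and a few extra tables. No additional patients are needed. The downside is a more modest claim for five countries.
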